## 4.3 Radiotherapy

4.3.1 Patient Positioning and Simulation: Patients will be simulated using CT simulation with or without contrast at the discretion of the treating physician. Immobilization will be employed at the discretion of the treating radiation oncologist.

4.3.2 Target Delineation:

- Gross Tumor Volume (GTV): the target lesion will be identified and delineated as GTV.
- Clinical Target Volume (CTV): areas at risk of subclinical disease around the GTV may be delineated at the discretion of the treating radiation oncologist.
- Planning Target Volume (PTV): 0.3-1 cm isotropic expansion from the GTV or CTV (if present).
- Diagnostic imaging including but not limited to CT, MR, and PET/CT imaging may be utilized to guide target delineation

4.3.3 Radiotherapy Planning:

- Each cycle of quad-shot radiotherapy will be comprised of 14.8 Gy in 4 fractions (3.7 Gy per fraction) delivered twice daily (at least 6 hours apart) over two consecutive days.
- All patients will receive 1 cycle of quad-shot radiotherapy between ICI cycles 2-3.
- Subsequent cycles may occur between immunotherapy cycles 6-7 and 11-12, if more than 1 cycle can be safely delivered at the discretion of the treating radiation oncologist. The eligibility for subsequent cycles will be at the discretion of the treating radiation oncologist.

Therefore, the total prescription dose will be:

- o 14.8 Gy in 4 fractions for those that complete 1 cycle (all patients will receive 1 cycle)
- o 29.6 Gy in 8 fractions for those that complete 2 cycles
- o 44.4 Gy in 12 fractions for those that complete 3 cycles

- Upon planning the initial cycle of quad-shot radiotherapy, a composite plan will be generated to assess the total dose to the target/organs at risk (see below).
  - o If deemed appropriate by the treating radiation oncologist, the same plan may be delivered for up to 3 cycles.
  - o If deemed appropriate by the treating radiation oncologist, re-simulation may be performed in order to plan subsequent cycles. This may be necessary to account for anatomic changes that may have occurred in the interim (between quad-shot cycles) which would otherwise impact dose to the target or organs at risk.

4.3.4 Organs at Risk (OAR): Organs at risk will vary depending on the location of the target lesion and will be delineated at the discretion of the treating radiation oncologist. No target or normal tissue constraints are mandated by this protocol. However, optional clinical goals are below:

Quad-Shot Radiotherapy in Combination with Immune Checkpoint Inhibition for  
 Advanced/Recurrent Head and Neck Cancer  
 Wake Forest Baptist Comprehensive Cancer Center  
 WFBCCC60320

Structure	Treatment Planning Goals	Treatment Planning Limit (if target is close to structure, higher doses may be accepted)
Spinal Cord	Max dose $\leq$ 37.2 Gy	same
Spinal Cord + 5mm	Max dose $\leq$ 39.2 Gy	39.2-40.6Gy to $<0.03\text{cc}$
Brachial Plexus	No more than 5% $>44.6$ Gy Max dose $\leq$ 47.4 Gy	No more than 5% $>49.2$ Gy Max dose $\leq$ 50Gy
GTV	97% of GTV receives the prescription dose	95% of GTV receives the prescription dose
	maximum dose no more than 110% of the prescription dose	maximum dose no more than 115% of the prescription dose
	100% of GTV receives 95% of prescription dose	99% of GTV receives 93% of prescription dose
Parotid gland ipsilateral to primary tumor site a	Mean dose $<26$ Gy	Mean dose $<30$ Gy
Parotid gland contralateral to primary tumor site a	Mean dose $<25.3$ Gy	Mean dose $<31.8$ Gy
Constrictors a	Mean dose $<37.2$ Gy; V39.6 $<33\%$ ; V44.5 $<15\%$	Mean dose $<44.5$ Gy; V46.9 $<50\%$ ;
Larynx a	Mean dose $<28.2$ Gy	Mean dose $<37$ Gy
Esophagus a	Mean dose $<28.1$ Gy; no hot spots in the esophagus	Mean dose $<31.2$ Gy; no hot spots in the esophagus
Lips a	Mean dose $<20$ Gy	Mean dose $<25$ Gy
Oral Cavity a	Mean dose $<28.1$ Gy; avoid hot spots $>44.5$ Gy	Mean dose $<34.2$ Gy; avoid hot spots $>44.5$ Gy
Mandible a	V44.5 $<20\%$ ; Max 47.4 Gy to mandible	V44.5 $<20\%$ ; Max 47.4Gy; minimize hot spots in the mandible
Submandibular gland(s) a	Mean $<33.6$ Gy	None

a GTV involving a non-critical OAR will be excluded from OAR contour – if applicable, OARx structure contour will represent X-GTV.

#### 4.3.5 Radiotherapy Delivery:

- External beam radiotherapy (photon or electron) will be delivered using 3D-conformal or intensity-modulated radiotherapy according to the treating radiation oncologist.
- Image guidance will be performed at the discretion of the treating physician.
- One cycle of quad-shot radiotherapy will be comprised of 14.8 Gy in 4 fractions (3.7 Gy per fraction) delivered twice daily (at least 6 hours apart) over two consecutive days.

#### 4.3.6 Radiotherapy Timing:

Quad-Shot Radiotherapy in Combination with Immune Checkpoint Inhibition for  
Advanced/Recurrent Head and Neck Cancer  
Wake Forest Baptist Comprehensive Cancer Center  
WFBCCC60320

- Radiation Therapy will be given as outlined in the Study Schema and according to the Study Calendar in Section 6.1:
  - Quad-shot Cycle #1: prior to cycle 4 (between pembrolizumab cycle 2-3 or 3-4) for all patients
  - Quad-shot Cycle #2 (if delivered): prior to cycle 8 (between pembrolizumab cycles 6-7 or 7-8)
  - Quad-shot Cycle #3 (if delivered): prior to cycle 13 (between pembrolizumab cycles 11-12 or 12-13).
- Radiotherapy is **NOT** to be given on the same day as immunotherapy/ICI infusion.
- Outside of this restriction, the timing of the delivery of 4 radiotherapy fractions that make up each cycle is not required.
- Though specific days are not mandated, it is **strongly recommended** that at least 1 day of the two consecutive days (including 2 of the 4 planned RT fractions per cycle) falls within 7 days prior to the delivery of an immunotherapy infusion.

## 4.4 Immunotherapy

Systemic immunotherapy will be delivered according to the standard of care for patients with recurrent/metastatic head and neck cancer.

### 4.4.1 Pembrolizumab Formulation/packaging/storage

Pembrolizumab will be obtained, stored, and administered in accordance with institutional guidelines.

### 4.4.2 Pembrolizumab Doses and treatment regimens

Pembrolizumab 200 mg will be given every 3 weeks to tumor progression or treatment tolerance.

### 4.4.3 Preparation of Pembrolizumab doses for administration with an IV bag

4.4.3.1 The dose of pembrolizumab for administration must be prepared by the Investigator's or site's designated IP manager using aseptic technique. Total time from needle puncture of the pembrolizumab vial to the end of administration should not exceed: 24 hours at 2°C to 8°C (36°F to 46°F) or 8 hours at room temperature (up to 25°C (77°F)). If in-use storage time exceeds these limits, a new dose must be prepared from new vials. Infusion solutions must be allowed to equilibrate to room temperature prior to commencement of administration.

4.4.3.2 Pembrolizumab will be administered at room temperature (approximately 25°C) by controlled infusion via an infusion pump into a peripheral or central vein. Following preparation of pembrolizumab, the entire contents of the IV bag should be administered as an IV infusion over approximately 30 minutes ( $\pm$ 5 minutes), using a 0.2, or 0.22- $\mu$ m in-line filter. Less than 25 minutes is considered a deviation.

4.4.3.3 The IV line will be flushed with a volume of IV solution (0.9% [w/v] saline) equal to the priming volume of the infusion set used after the contents of the IV bag are

Quad-Shot Radiotherapy in Combination with Immune Checkpoint Inhibition for  
Advanced/Recurrent Head and Neck Cancer  
Wake Forest Baptist Comprehensive Cancer Center  
WFBCCC60320

fully administered, or complete the infusion according to institutional policy to ensure the full dose is administered and document if the line was not flushed.

4.4.3.4 Standard infusion time is 30 minutes. However, if there are interruptions during infusion, the total allowed time should not exceed 8 hours at room temperature.

#### **4.4.4 Monitoring of dose administration**

4.4.4.1 Subjects will be monitored before, during and after the infusion with assessment of vital signs at the times specified in the Schedule of Assessment. Subjects are monitored (pulse rate, blood pressure) every 30 minutes during the infusion period (including times where infusion rate is slowed or temporarily stopped).

4.4.4.2 In the event of a ≤Grade 2 infusion-related reaction, the infusion rate of study drug may be decreased by 50% or interrupted until resolution of the event (up to 4 hours) and re-initiated at 50% of the initial rate until completion of the infusion. For subjects with a ≤Grade 2 infusion-related reaction, subsequent infusions may be administered at 50% of the initial rate. Acetaminophen and/or an antihistamine (e.g., diphenhydramine) or equivalent medications per institutional standard may be administered at the discretion of the investigator. If the infusion-related reaction is Grade 3 or higher in severity, study drug will be discontinued. The standard infusion time is thirty minutes, however if there are interruptions during infusion, the total allowed time from infusion start to completion of infusion should not exceed 8 hours at room temperature, with maximum total time at room temperature not exceeding 8 hours (otherwise requires new infusion preparation).

4.4.4.3 As with any antibody, allergic reactions to dose administration are possible. Appropriate drugs and medical equipment to treat acute anaphylactic reactions must be immediately available, and study personnel must be trained to recognize and treat anaphylaxis. The study site must have immediate access to emergency resuscitation teams and equipment in addition to the ability to admit subjects to an intensive care unit if necessary.

#### **4.4.5 Accountability and dispensation**

Drug accountability logs will be maintained for the investigative agent used under this protocol. These logs shall record quantities of study drug received and quantities dispensed to patients, including lot number, date dispensed, patient identifier number, patient initials, protocol number, dose, quantity returned, balance remaining, and the initials of the person dispensing the medication.

#### **4.4.6 Dose Modification and Toxicity Management**

4.4.6.1 For adverse events (AEs) that are considered at least partly due to administration of pembrolizumab, the following dose adjustment guidance may be applied:

4.4.6.1.1 Treat each of the toxicities with maximum supportive care (including holding the agent suspected of causing the toxicity where required). Isolated increase in amylase has been noted after radiotherapy for the head and neck cancer, being released

Quad-Shot Radiotherapy in Combination with Immune Checkpoint Inhibition for  
Advanced/Recurrent Head and Neck Cancer  
Wake Forest Baptist Comprehensive Cancer Center  
WFBCCC60320

from the salivary glands included in the radiation field. In addition, asymptomatic increase in the lipase has been reported. If the patient does not have symptoms of pancreatitis, treatment with pembrolizumab does not need to be stopped when increase in amylase and/or lipase are identified. Follow up of the lab values until normalization is recommended.

- 4.4.6.1.2 If the symptoms promptly resolve with supportive care, consideration should be given to continuing the same dose of pembrolizumab along with appropriate continuing supportive care.
- 4.4.6.1.3 Otherwise, pembrolizumab should be permanently discontinued. Dose reductions are not permitted.

4.4.6.2 Based on the mechanism of action of pembrolizumab leading to T-cell activation and proliferation, there is the possibility of observing immune related Adverse Events (irAEs) during the conduct of this study. Potential irAEs include immune-mediated enterocolitis, dermatitis, hepatitis, and endocrinopathies. Subjects should be monitored for signs and symptoms of irAEs. In the absence of an alternate etiology (e.g., infection or PD) signs or symptoms of enterocolitis, dermatitis, hepatitis, and endocrinopathy should be considered to be immune-related.

4.4.6.3 All toxicities will be graded according to NCI CTCAE v 5.0.

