### **6.6 Criteria for Removal from Study**

Patients will be removed from study when any of the following criteria apply:

Quad-Shot Radiotherapy in Combination with Immune Checkpoint Inhibition for Advanced/Recurrent Head and Neck Cancer  
Wake Forest Baptist Comprehensive Cancer Center  
WFBCCC60320

- Patient withdrawal of consent or loss to follow-up.
- Adverse event that, in the opinion of the investigator or the sponsor, contraindicates further dosing.
- Subject is determined to have met one or more of the exclusion criteria for study participation at study entry and continuing investigational therapy might constitute a safety risk.
- Pregnancy or intent to become pregnant
- Grade  $\geq 3$  infusion reaction.
- Subject noncompliance that, in the opinion of the investigator or sponsor, warrants withdrawal; eg, refusal to adhere to scheduled visits.
- Initiation of alternative anticancer therapy including another investigational agent.
- Confirmation of PD and investigator determination that the subject is no longer benefiting from protocol treatment.
- Death.

Subjects who are permanently discontinued from further receipt of investigational product, regardless of the reason (withdrawal of consent, due to an AE, other), will be identified as having permanently discontinued treatment.

Subjects who are removed from study prior to completing at least 2 cycles of ICI followed by at least 1 cycle of quad-shot radiotherapy followed by at least 2 cycles of ICI will be discontinued from the study and replaced.

Subjects who are permanently discontinued from receiving investigational product will be followed for safety until follow-up criteria are met in Section 6.4. Subjects who decline to return to the site for evaluations will be offered follow-up by phone for at least 60 days as an alternative.

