### **Severe and Fatal Immune-Mediated Adverse Reactions**

Immune-mediated adverse reactions, which may be severe or fatal, can occur in any organ system or tissue and usually occur during treatment; however, they can also occur after discontinuation. Early identification and management are essential to ensuring safe use of PD-1-blocking antibodies. Monitor for symptoms and signs of immune-mediated adverse reactions. Evaluate clinical chemistries, including liver tests and thyroid function tests, at baseline and periodically during treatment. Institute medical management promptly to include specialty consultation as appropriate.

In general, withhold pembrolizumab for Grade 3 or 4 and certain Grade 2 immune-mediated adverse reactions. Permanently discontinue pembrolizumab for Grade 4 and certain Grade 3 immune-mediated adverse reactions. For Grade 3 or 4 and certain Grade 2 immune-mediated adverse reactions, administer corticosteroids (1 to 2 mg/kg/day prednisone or equivalent) or other appropriate therapy until improvement to Grade 1 or less followed by a corticosteroid taper over 1 month. Consider administration of other systemic immunosuppressants in patients whose immune-mediated adverse reaction is not controlled with corticosteroids. Institute hormone replacement therapy for endocrinopathies as warranted.

**Immune-mediated pneumonitis:** Immune-mediated pneumonitis occurred in about 2.5% of the patients treated with immune checkpoint inhibitors and leads to permanent discontinuation of the drug in about half of the patients. Systemic corticosteroids are required in all patients with pneumonitis. Withhold pembrolizumab for Grade 2, and permanently discontinue for Grade 3 or 4. Resume in patients with complete or partial resolution (Grade 0 to 1) after corticosteroid taper.

**Immune-mediated colitis:** Immune-mediated colitis occur in about 1% of patients receiving immune checkpoint inhibitors leading to permanent discontinuation pembrolizumab in a small percent of patients. Systemic corticosteroids are required in all patients with colitis. Withhold pembrolizumab for Grade 2 or 3, and permanently discontinue for Grade 4. Resume in patients with complete or partial resolution (Grade 0 to 1) after corticosteroid taper.

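### Sections 4.4.6 and 8.1 give opposite instructions on restarting pembrolizumab after toxicity that does not resolve promptly, and nothing says which section governs

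*Combined protocol and SAP*

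**What the plan says.** Section 4.4.6.1 covers adverse events considered at least partly due to pembrolizumab. Its lead-in is permissive: "the following dose adjustment guidance may be applied". Supportive care comes first, "including holding the agent suspected of causing the toxicity where required". Two outcomes follow. The first is "If the symptoms promptly resolve with supportive care, consideration should be given to continuing the same dose of pembrolizumab". The second is "Otherwise, pembrolizumab should be permanently discontinued", with dose reduction ruled out. Neither depends on grade or organ, *promptly* is not defined, and there is no rule for resuming after a hold.

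Section 8.1, under Severe and Fatal Immune-Mediated Adverse Reactions, sets rules by organ and grade. For colitis it says "Withhold pembrolizumab for Grade 2 or 3, and permanently discontinue for Grade 4", and then "Resume in patients with complete or partial resolution (Grade 0 to 1) after corticosteroid taper". The same resumption sentence appears for pneumonitis, hepatitis, nephritis, dermatologic reactions and the group of other reactions. The general paragraph sets the steroid taper at one month. Endocrinopathies have a separate rule: the drug is withheld only where clinically necessary, at Grades 2 to 4.

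Section 6.6 lists, among the grounds for removal, an adverse event that the investigator or sponsor judges to rule out further dosing. It applies replacement to "Subjects who are removed from study prior to completing at least 2 cycles of ICI", then one quad-shot cycle, then two more ICI cycles. Section 4.2 is broader and replaces any patient who does not complete study treatment and investigations.

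**The concern.** Two parts of one protocol address the same clinical situation and point in opposite directions. Under 4.4.6, a patient whose immune-related event needs a hold and a steroid course, and does not clear promptly, comes off pembrolizumab for good. Under 8.1, the same patient may restart. Neither section refers to the other, and no text ranks them.

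What is at stake first is safety and consistency of care: two clinicians could each follow the protocol and treat the same event differently. It also affects treatment received, and hence how the tolerability objective (2.2.6) is read, since stopping for toxicity would partly reflect which section was consulted. Who is evaluable for the primary response rate could also be affected, but only by a longer route, set out below.

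**Working it through.** No figure in the plan is in dispute. The one related figure, in 11.3, reproduces. The exact 95% Clopper-Pearson interval for 7/15 has lower limit Beta quantile(0.025; 7, 9) = 0.213 and upper limit Beta quantile(0.975; 8, 8) = 0.734. The width is 0.734 - 0.213 = 0.521, which matches the stated 0.52. The contradiction does not change it.

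**Step 1: the two sections side by side, for an event that does not resolve promptly.**

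| Event | Section 8.1 | Section 4.4.6 | Result |
|---|---|---|---|
| Pneumonitis, Grade 2 | Withhold, resume | Permanent stop | Conflict |
| Pneumonitis, Grade 3-4 | Permanent stop | Permanent stop | Agree |
| Colitis, Grade 2-3 | Withhold, resume | Permanent stop | Conflict |
| Colitis, Grade 4 | Permanent stop | Permanent stop | Agree |
| Hepatitis, AST/ALT above 3 and up to 10 x ULN, or bilirubin up to 3 x ULN | Withhold, resume | Permanent stop | Conflict |
| Hepatitis above those limits | Permanent stop | Permanent stop | Agree |
| Nephritis, dermatologic, other: Grade 3 | Withhold, resume | Permanent stop | Conflict |
| Nephritis, dermatologic, other: Grade 4 | Permanent stop | Permanent stop | Agree |
| Endocrinopathy, Grade 2-4 | Withhold only if clinically necessary | Permanent stop | Conflict |

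The conflict is therefore confined to events that 8.1 would hold and restart, or would not necessarily hold. The grade at which it arises differs by organ: Grade 2 is a stated hold grade for pneumonitis and colitis, but Grade 3 is the hold grade for nephritis, dermatologic and other reactions.

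**Step 2: can prompt resolution cover a steroid taper?** Section 4.4.2 gives pembrolizumab every 3 weeks, or 21 days. The 8.1 taper lasts one month, about 30 days, and starts only once the event has improved to Grade 1 or less. Since 30 > 21, a hold through the taper spans at least one scheduled infusion. That is hard to call prompt, and 4.4.6 does not say that a steroid course counts as supportive care.

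**Step 3: the route to evaluability.** Section 11.3 counts 15 patients evaluable under 7.1.1, whose note repeats the 6.6 replacement rule. For the choice of section to change who is replaced under 6.6, three things must happen:

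1. The event falls in a conflict row above.
2. The patient is removed from study, on the investigator's or sponsor's judgement. Section 6.6 separately identifies patients who permanently discontinue the drug and keeps them in safety follow-up, so stopping the drug is not in itself removal.
3. Removal comes before 2 ICI cycles, one quad-shot cycle and 2 further ICI cycles are complete. That means before completion of the fourth ICI cycle if quad-shot falls between cycles 2 and 3 (2 + 2 = 4), or of the fifth if it falls between cycles 3 and 4 (3 + 2 = 5).

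Later events change treatment received but not replacement under 6.6. Section 4.2 has no such window and could reach them, depending on what completing study treatment is taken to mean.

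**The case against.** The best defence is that these are not two binding rules. Section 4.4.6.1 is guidance that may be applied, it allows the drug to be held, and it leaves *promptly* open. Section 4.4.6.2 takes up immune-related events separately without a stopping rule, so a reader could treat 8.1 as the specific instruction and 4.4.6.1 as the general one. Sections 4.4 and 6.3 place pembrolizumab under standard of care, and 6.4 contemplates treatment delays for adverse events.

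This softens the conflict but does not remove it. Permissive wording still leaves two unranked instructions. That the specific prevails over the general is an inference that the protocol never states, and 4.4.6.1 covers every pembrolizumab-related event without excepting immune-related ones.

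Two stronger readings are tempting, and the documents do not support them. A reader might infer that the section followed decides who stays in the response denominator. It does not do so directly: removal rests on judgement, and 6.6 replacement has the early window described above. The replacement rules would also remain an issue after 4.4.6 and 8.1 were aligned.

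A reader might also estimate about one affected patient in 15, either from the 5% discontinuation figure in 8.1 (0.05 x 15 = 0.75) or by adding the reaction rates there (2.5 + 1 + 2 + 0.5 + 2 = 8%; 0.08 x 15 = 1.2). The 5% counts permanent discontinuations, not patients whom one section would restart and the other stop. It also overlaps the reaction rates, since pneumonitis and hepatitis are among its listed causes. The reaction rates are not split by grade, and they include cases that already end in a permanent stop (about half for pneumonitis and nephritis). They are not limited to the early window either.

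**Conclusion.** The contradiction stands as a matter of text. For events that 8.1 would withhold and resume, and that do not resolve promptly, 4.4.6 and 8.1 give opposite instructions. For endocrinopathies, 4.4.6 defaults to a permanent stop where 8.1 withholds only if needed. Where 8.1 itself requires a permanent stop, the sections agree.

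The main consequence is for patient safety and treatment received. The effect on evaluability is secondary and conditional. Its size cannot be estimated reliably, because the documents give neither the share of events in the conflicting grades, nor how many fail to resolve promptly, nor how many would lead to early removal. The conclusion assumes only that a hold through a one-month taper is not prompt resolution. No sample-size or precision figure is wrong, and no view is taken on which clinical rule is right.

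**What to change.** Reconcile 4.4.6 with 8.1 so that one section governs and the other refers to it. State how the general guidance applies to immune-related events, and whether a hold with a steroid course counts as supportive care. The sponsor decides the clinical content.

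Record the reason for every pembrolizumab hold or permanent stop, and whether removal or replacement followed, so that any effect on evaluability can be reported. Section 13.2 already lists an adverse events log, cycle tracking and off-treatment forms. Their fields are not shown, so at most a field or two would be added. The cost is protocol wording and possibly a small form change, with no effect on sample size.
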